For in vitro assay, the relevant standard curve will be used to estimate a CTC concentration in the blood of each melanoma subject. On the same subject, the CTC counts per minute obtained from in vivo Cytophone monitoring will be converted into a CTC concentration using the blood-flow rate obtained from Doppler ultrasonography on the same vein region. Data will be transformed to their base-10 logarithms both to reduce heteroscedasticity and to facilitate inference on fold-change differences. Agreement between in vivo and in vitro methods will be assessed using the methods of Bland and Altman. Specifically, for the in vivo method and in vitro method, the average and difference in CTC counts between methods will be calculated for each subject and plotted in a Bland-Altman plot. The 95% limits of agreement between in vivo PAFC and in vitro method will be calculated from the difference in CTC counts as the mean ± 2 standard deviations. The mean difference in CTC counts between in vivo and in vitro method will be reported along with a two-sided 95% confidence interval. The mean differences of 5-fold or less will be considered good concordance between in vivo and the in vitro methods, whereas mean differences of 10-fold or more will be considered cause for concern.

Sample size considerations: For the primary analysis of the Group 1, we will use a mixed- models repeated-measures approach to estimate the skin-pigmentation group means and symmetric two-sided 90% confidence intervals for measurements from the hand of each study subject. The half-widths of the confidence intervals (a.k.a. the 90% margins of error on the means, or 90% MEMs) will depend heavily both on the number of subjects in a given skin-pigmentation group and on the intra-subject correlation among individual PA contrasts. **Figure 5** shows how the 90% MEMs vary with intra-subject correlation for exemplar skin-pigmentation group sizes of 3, 5, and 7 per group when the total sample size is 30 healthy volunteers. The 90% MEMs (in SD units) are for the group means of measurements taken from the hands of study subjects. They are calculated using the method of Donner under the assumptions (1) that PA contrasts will be determined on exactly 2 vessels per hand or exactly 3 vessels per hand, and (2) that the denominator degrees of freedom will be 12 based on all three skin-pigmentation groups being represented among the 30 study subjects. Inasmuch as the intra-subject correlation is unlikely to

be >0.5, the range of 90% margins of error shown in Figure D indicate that 30 healthy volunteers should provide sufficient precision to meet its research goals. For Groups 2-4, a sample size of 50 melanoma subjects produces a symmetric two-sided 95% confidence interval on the mean difference between methods that has a half-width of 0.258 SD units, where one SD unit is one standard deviation of the difference between methods. In each group, the CTC detection rates via the in vivo Cytophone versus the in vitro methods will be compared in fifty samples from melanoma subjects via one-sided McNemar's test at 5% alpha to determine whether in vivo diagnosis has a significantly increased detection rate. To calculate power of the planned test, we assume that, when the two methods produce a discordant pair of results on the same sample (i.e., when the in vivo Cytophone disagrees with the in vitro method on whether CTCs have been detected), the odds ratio is 10-fold in favor of *in vivo* data having detected the CTCs. Figure 6 shows how power to detect the 10-fold odds ratio varies with the proportion of discordant pairs of assay results among a fixed sample size of N=50 melanoma subjects. Since the subjects with a current or recent history of melanoma are expected to have CTCs but have them at concentrations at or below the detection limits of existing *in vitro* assay methods, the proportion of discordant assay-result pairs among subjects should be quite high if in vivo Cytophone works as advertised. Figure 6 demonstrates that 50 subjects should provide sufficient power to meet the proposed research goals.

Data Storage

Individual information will be protected in all data resulting from this study. No personal information will be collected other than basic demographic descriptors. The Cytophone's results will be analyzed and documented. All data (completed instrument tools and observation notes) will be kept confidential. Original data will be kept on a password protected computer, stored in a locked cabinet in the researcher's office and destroyed three years after completion of the research.

Bibliography

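### Good concordance is declared from the mean fold-difference alone, which measures average bias and could pass methods that differ 10-fold or more in many individual patients

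*Protocol*

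**What the plan says.** The rule is in the Protocol, Data Analysis and Evaluation Techniques, in the analysis plan for Groups 2-4. CTC concentrations from both methods are put on the log scale: "Data will be transformed to their base-10 logarithms both to reduce heteroscedasticity and to facilitate inference on fold-change differences". The stated framework is "Agreement between in vivo and in vitro methods will be assessed using the methods of Bland and Altman". The limits of agreement "will be calculated from the difference in CTC counts as the mean ± 2 standard deviations", and the mean difference "will be reported along with a two-sided 95% confidence interval".

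The only verdict attached to this analysis concerns the mean: "The mean differences of 5-fold or less will be considered good concordance between in vivo and the in vitro methods". The other end of the scale is flagged in the same sentence, again on the mean only, with 10-fold as the bound.

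No acceptance limit is set for the limits of agreement, and the confidence interval plays no part in the verdict. A mean between 5-fold and 10-fold is given no reading.

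Earlier in the same plan, pairs positive by both methods are summarised by number, mean and SD, again without a criterion. The sample size section gives precision for the mean difference only.

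**The concern.** The mean of the log10 differences answers whether one method reads higher than the other on average. It does not show how close the two readings are in a given patient. One patient reading 20-fold higher in vivo and another reading 20-fold lower contribute a mean ratio of exactly 1. A rule on the mean alone therefore places no upper bound on the spread of individual differences, which is what limits of agreement exist to describe.

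The rule also uses a point estimate. An observed mean at or below 5-fold earns the label however wide its interval is, even if the interval reaches the 10-fold bound that the protocol itself regards as worrying.

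At stake is the meaning of a prespecified conclusion. A report could state good concordance, as the protocol defines it, next to limits of agreement that show the opposite.

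**Working it through.** **Inputs from the protocol.** Good: mean difference of at most 5-fold, which is log10(5) = 0.699. Concern: at least 10-fold, which is log10(10) = 1. Limits of agreement: mean ± 2 SD on the log10 scale. Number of subjects: 50 per group.

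**Input not in the protocol.** The SD of the between-method log10 difference is used only as a unit and has no numeric value. I assume 0.5 to 1.0 log10 units and normally distributed differences.

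**The protocol's own figure.** The sample size section gives a 95% half-width of 0.258 SD for 50 subjects. The usual formula is t(0.975, n−1)/√n. At n = 50 it gives 0.284 (0.277 with the normal quantile); 0.258 is the value for n = 60. The stated figure is not reproduced. This does not affect the point here, and I use 0.284 below.

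**Scatter that the rule lets through.** With mean log10 difference m, the share of patients differing by more than 10-fold is 1 − Φ((1 − m)/SD) + Φ((−1 − m)/SD). The limits of agreement are 10^(m ± 2 SD).

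| True mean ratio | SD (assumed) | Limits of agreement | Patients beyond 10-fold |
|---|---|---|---|
| 1 | 0.5 | 0.1 to 10 | 4.6% |
| 1 | 0.7 | 0.04 to 25 | 15% |
| 1 | 1.0 | 0.01 to 100 | 32% |
| 3 | 0.5 | 0.3 to 30 | 15% |
| 3 | 1.0 | 0.03 to 300 | 37% |

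For a 5-fold difference at zero bias, 2 × (1 − Φ(0.699/SD)) gives 16% at SD 0.5 and 48% at SD 1.0.

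**What the rule would say.** With 50 pairs, the probability that the observed mean falls within 5-fold is about 100% in every row with ratio 1. At ratio 3 it is 94% for SD 1.0 and higher for smaller SDs. Every row would almost always be labelled good.

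**At the edge of the rule.** With an observed mean of exactly 5-fold, the upper limit of agreement passes 10-fold once 0.699 + 2 SD > 1, that is, for any SD above 0.15.

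**Effect of ignoring the interval.** At SD 1.0 and n = 50, an observed 5-fold mean has a 95% interval of 10^(0.699 ± 0.284), or 2.6- to 9.6-fold. A log difference needs a positive result from both methods, and the sample size section expects many discordant pairs, so fewer than 50 pairs may be usable. At an illustrative 15 pairs the half-width is 2.145/√15 = 0.554, and the interval is 1.4- to 18-fold: labelled good, yet compatible with the protocol's own concern bound.

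**Comparison within the protocol.** For the two lasers, equivalence is claimed only if both ends of a 90% confidence interval lie inside the window. The rule for the two CTC methods is looser, without a stated reason.

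**The case against.** The strongest reply is that nothing is hidden. The Bland-Altman plot, the limits of agreement and the interval are all planned, so a 100-fold spread would be plain to any reader. Agreement with the in vitro assay is in none of the stated objectives, no action follows from the label, and the Background presents the device as a supplement to established diagnosis. This stands in part. It confines the defect to the verdict sentence, but it does not rescue a rule that can call poor individual agreement good.

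Three stronger readings are tempting and not supported.

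- A reader might infer that widely scattered methods will be declared concordant. The rule only permits this; how often it happens depends on an SD that the protocol does not give.
- A reader might infer that the methods could not stand in for each other in any single patient. At SD 0.5 and no bias, about 84% of patients agree within 5-fold and about 95% within 10-fold.
- A reader might infer that the CTC thresholds in the second primary objective are undermined. The protocol derives those by linking Cytophone counts to medical records and outcomes, so they do not rest on agreement with the in vitro assay.

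A further objection concerns the remedy. The 5-fold figure was set for a mean, and moving it onto the limits of agreement would require an SD of at most 0.699/2 = 0.35 even at zero bias, a choice with no basis in the document. Sampling volume matters too: one cell in the 10 mL in vitro sample reads as 100 per litre, while the device is said to reach 1 per litre, so large individual differences can come from the comparator's volume. Both points stand. They are reasons for the sponsor to choose and justify the limit, not reasons to have none.

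**Conclusion.** The point holds as a defect in a stated decision rule. Good concordance rests on the point estimate of average bias, with no bound on individual differences and no use of the planned interval. At zero bias the rule passes methods for which 4.6% (SD 0.5) to 32% (SD 1.0) of patients differ by more than 10-fold. These percentages assume normal log10 differences and an SD that I supplied. That the rule sets no ceiling on the SD needs neither assumption.

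The Background gives some reason to expect appreciable scatter. It reports 60% to 97% cell loss in sample processing, so recovery of 40% to 3%, about a 13-fold range (40/3). Part of that may lie between assays, so it does not fix the SD. The unclassified zone between 5-fold and 10-fold is a minor addition. The rule should be changed before data are seen.

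**What to change.** Change the wording in the analysis plan for Groups 2-4:

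1. Relabel the 5-fold and 10-fold criteria on the mean as criteria for average bias. Call bias acceptable only if the whole 95% confidence interval lies within 5-fold in either direction, as the protocol already requires of the interval for laser equivalence. With 50 pairs and SD 1.0, the observed mean would then have to be at most 10^(0.699 − 0.284) = 2.6-fold.
2. Base any statement of concordance on the planned 95% limits of agreement. Report them with their confidence intervals and the number of pairs positive by both methods, and judge them against a fold limit that the sponsor prespecifies and justifies in view of the 10 mL in vitro volume. One example is both limits within the existing 10-fold bound, which allows an SD of at most 0.50 at a mean ratio of 1, 0.35 at 2-fold, 0.26 at 3-fold and 0.15 at 5-fold.
3. State that results between 5-fold and 10-fold are intermediate.

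The cost is a few sentences. No new data or procedures are needed, and every point estimate involved is already planned; only the confidence intervals of the limits are added. The downside is that the label good concordance becomes harder to earn.

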Figure 5. 90% Margin of MEM versus intra-subject correlation for exemplar skin-pigmentation group sizes of 3, 5, and 7 per group when the total sample size is 30. The 90% MEMs (in SD units) are for the group means of measurements taken from the hands of study subjects. They are calculated using the method of Donner under the assumptions (1) that PA contrasts will be determined on exactly 2 vessels/hand ("O" symbols) or exactly 3 vessels/hand ("X" symbols) and (2) that the denominator degrees of freedom will be 12 based on all three skin-pigmentation groups being represented among the 30 study subjects.

Figure 6. Power versus proportion of discordant pairs of assay results among N=30 total samples from melanoma subjects when the odds ratio among discordant pairs is 10-fold in favor of the Cytophone showing the positive detection result. Power is power of the one-sided McNemar's test at 5% alpha.
